2.4.1 Clinical Data/EMR Abstraction

Intervention Group

Phase1 (Titration) Clinical: HbA1c will serve as the primary outcome and clinical measure to determine the impact of the MDC-T app on glycemic control from baseline to 3 months. Related measures to be collected will include: Change in FBG from baseline to 3 months, rate of patients who attained individualized titration target, the time it took to attain titration target and number and type of hypoglycemic events, which are defined as follows:

- Mild/asymptomatic hypoglycemia blood glucose <70 mg/dl and no symptoms;
- Moderate/symptomatic hypoglycemia blood glucose <70 mg/dl and symptoms;
- Severe/symptomatic hypoglycemia requires assistance of another person to resuscitate because blood glucoses are too low to maintain consciousness.

Hypoglycemic data will be collected in the following ways:

1) ask the patient to contact study team if/when it happens,

- 2) ask patient at each study visit,
- 3) review of MDC information,
- 4) review of EMR,

Data will be collected on an AE form for each patient and reported if an SAE. In addition, blood pressure, cholesterol and BMI data will be retrieved from the patient's EMR record.

Phase 2 (Maintenance) Clinical: HbA1c will serve as the primary outcome to determine the longer term impact of MDC-M app on maintenance of glycemic control from 3 months to 6 months for those patients achieving glycemic targets during the MDC-T titration phase. Related measures to be collected will include the number of patients who maintained individualized glycemic targets, change in FBG from 3 months to 6 months, and record of reported hypoglycemic events (following same definitions and data collection plan as described for Phase 1). Additionally, blood pressure, cholesterol and BMI data will be retrieved from the patient's EMR record.

All of the aforementioned data will be collected for the intervention group in accordance with the study calendar in section 2.2.5.

Control Group

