A majority of the data is also expected to be available within the EMR for the control group. HbA1c, FBG, blood pressure, cholesterol, and BMI data should be recorded and accessible for patients. In addition, many patients also have BG meter readings. At a minimum, we will select patients who have HbA1c values that correspond to baseline [index date = date of insulin initiation] and follow-up time points/time frames that correspond with those described in the study calendar (section 2.2.5). EMR records, including notes, downloads, and related documented data will be reviewed to identify and classify hypoglycemic events according to already aformentioned definitions.

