2.5 Study Endpoints

2.5.1 Primary Endpoint

Change in HbA1c at 3 months as compared to patients using standard of care.

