2.6 Statistical Analysis

2.6.1 Power and Sample Size Justification

The primary objective of this study is to estimate the difference in HbA1c between the study treatment groups at 3 months. The sample size justification is based on precision estimate (i.e., confidence interval for the HbA1c difference between groups). The expected standard deviation for the 3-months change from baseline in HbA1c is 1.5. With 109 patients in the interventional arm and 109 patients in the retrospective control arm, the treatment effect, expressed as the LS means difference between arms, would be estimated with an expected precision of \pm 0.40. Additionally, this sample size allows for a sufficient number of patients after drop-out, loss to follow-up and/or missing data to enter the maintenance phase (Phase 2) of the study. Based on previous research and experiences with insulin titration, an anticipated 70% of patients (n=76) will enter Phase 2 of the study.

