2.6.2 Data Analysis

Patients will be matched 1:1 on a propensity score based on baseline demographics and clinical characteristics to improve the comparability of the interventional and retrospective groups. A logistic regression model will be used to estimate the propensity score and those baseline variables that influence treatment assignment will be included in the model. In this analysis, the following variables will be used to calculate the propensity score: age, gender, baseline BMI and baseline HbA1c. Other factors that may be included are race and number of comorbid conditions. Once the propensity score is calculated, a greedy nearest neighbor algorithm will be used for matching to form pairs of subjects from intervention and control groups with similar propensity scores. This means that for a given treated subject, the closest untreated subject within the specified caliper distance is selected for matching to the treated subject.

Descriptive statistics (e.g., demographics, duration of diabetes, etc.) will be used to describe the study groups. Baseline comparisons will be examined using standardized mean differences. A linear mixed model will be used to adjust the fixed effect of baseline FBG and the random effect of matched pairs, allowing to estimate the treatment effect with 95% CI. . Generalized estimating equations (GEE) for binary outcomes will be for binary outcomes to compare the change in slopes of outcomes of interest between the two groups and account for matched pairs . In addition, for the intervention group only, descriptive statistics will be used to summarize other data (e.g., patient and provider surveys, MDC metrics, etc.), and thematic analysis of any qualitative findings will be made.

Phase 1 (Titration): For the intervention group only, using a descriptive statistical approach, a primary assessment of titration outcomes will be built into the study at 3 months to evaluate the MDC-T app using a combination of clinical data, provider and patient feedback and process data (including patient/provider study-specific efficiency and satisfaction surveys, DE logs, validated DMSRQ-SF and MDC analytics).

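### The only linear outcome model adjusts for baseline FBG but not baseline HbA1c, although HbA1c change is the primary endpoint; adding it costs one model term

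*Combined protocol and SAP*

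**What the plan says.** The protocol makes HbA1c the main result in three places. Section 2.5.1 defines the primary endpoint as "Change in HbA1c at 3 months as compared to patients using standard of care". Section 2.4.1 says that "HbA1c will serve as the primary outcome and clinical measure to determine the impact of the MDC-T app on glycemic control". Section 2.6.1 opens with "The primary objective of this study is to estimate the difference in HbA1c between the study treatment groups at 3 months" and continues that "the treatment effect, expressed as the LS means difference between arms, would be estimated with an expected precision of" ±0.40.

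Section 2.6.2 gives the analysis. For the match, "the following variables will be used to calculate the propensity score: age, gender, baseline BMI and baseline HbA1c"; race and a comorbidity count are optional, and baseline FBG is not listed. Balance is then inspected: "Baseline comparisons will be examined using standardized mean differences". No action is stated if a difference is large. The outcome model follows: "A linear mixed model will be used to adjust the fixed effect of baseline FBG and the random effect of matched pairs", and it is to yield the treatment effect with a 95% interval. The sentence names no outcome. The only other between-group model is a GEE for binary outcomes, with no covariates named.

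Baseline HbA1c is on hand for everyone. HbA1c above 7.5% is an entry criterion in both groups (3.2.1, 3.2.2), and for controls 2.4.1 states: "At a minimum, we will select patients who have HbA1c values that correspond to baseline".

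**The concern.** The mixed model in 2.6.2 is the only one in the plan that can produce the LS means difference promised in 2.6.1, so on a fair reading it serves the primary endpoint. Its one named covariate is a different glycaemic measure from the one being analysed. Baseline HbA1c is part of the change score and can be expected to correlate with it, but it enters as a covariate only through the propensity score, as one of at least four variables.

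Matching on a composite score balances groups on average. It does not make the two members of a pair alike in HbA1c, so the random pair effect does not stand in for the covariate. Chance imbalance that survives matching goes into the FBG-only estimate, reduced only as far as FBG tracks HbA1c. In a non-randomised comparison with a retrospective control group, that protection is worth having when it is available at no cost.

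**Working it through.** **1. The plan's own figure.** Inputs: SD of change 1.5 and 109 per arm (2.6.1), 95% interval (2.6.2).

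- Half-width = 1.96 × 1.5 × √(2/109) = 0.398; with t on 216 df, 0.4005.
- Solving for n: 2 × (1.96 × 1.5 / 0.40)² = 108.04, rounded up to 109.

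The ±0.40 reproduces. It is the independent two-sample formula with no covariate and no pairing, so it does not depend on the missing term.

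**2. Formula check, ignoring matching.** Let r be the size of the correlation between baseline HbA1c and HbA1c change, and ρ the correlation of FBG with HbA1c. The documents give neither; take ρ = 0.6, with FBG acting on change only through HbA1c.

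- FBG alone, 0.4005 × √(1 − (ρr)²): 0.389 at r = 0.4 and 0.374 at r = 0.6.
- HbA1c, 0.4005 × √(1 − r²): 0.367 and 0.320.
- At r = 0 there is no gain: the lost degree of freedom moves 0.400 to 0.401.

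**3. Simulation of the matched design.** From the plan: 109 treated, SD 1.5, propensity model on age, gender, BMI and HbA1c, greedy 1:1 nearest-neighbour matching within a caliper, random pair effect. Assumed for the base case: 400 candidate controls, pre-match shifts of 0.3 SD in HbA1c and 0.2 SD in age and BMI, caliper 0.2 SD of the logit, ρ = 0.6. There were 2,000 replicates per cell, with 107.3 pairs on average.

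| r | Half-width, FBG | Half-width, FBG + HbA1c | True SD, no covariate | True SD, FBG | True SD, FBG + HbA1c | Fall in true SD, FBG to both |
|---|---|---|---|---|---|---|
| 0.2 | 0.392 | 0.388 | 0.2025 | 0.2029 | 0.2021 | 0.4% |
| 0.4 | 0.380 | 0.363 | 0.1920 | 0.1937 | 0.1890 | 2.4% |
| 0.6 | 0.357 | 0.317 | 0.1730 | 0.1770 | 0.1650 | 6.8% |

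The true sampling SD is the fairer measure. Half-widths fall more because matching has already balanced HbA1c between groups and the model without HbA1c does not fully credit that. Across pools of 200–400, shifts of 0.3–0.6 SD and, in the base pool, ρ = 0.8, the fall in true SD is 2.0–2.6% at r = 0.4 and 5.2–7.2% at r = 0.6. If FBG has its own standardised effect of 0.15 beside 0.4 for HbA1c, the SDs are 0.1846 (none), 0.1830 (FBG) and 0.1781 (both), which supports keeping FBG and adding HbA1c.

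**4. Imbalance left after matching.** The shift in the FBG-only estimate per 0.1 SD of HbA1c imbalance is r × 1.5 × 0.1 × (1 − ρ²).

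- ρ = 0.6: 0.4 × 0.15 × 0.64 = 0.038 and 0.6 × 0.15 × 0.64 = 0.058. Simulated slopes are 0.037 and 0.056, and 0.000 with HbA1c added.
- ρ = 0.8: 0.4 × 0.15 × 0.36 = 0.022 and 0.6 × 0.15 × 0.36 = 0.032.

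The median within-pair HbA1c gap is 0.68 SD (0.45–0.69 across scenarios). A standardised HbA1c difference above 0.1 remains in 1.6–9.3% of replicates (9.3% in the base case). In those base-case replicates the FBG-only mean error is 0.060 points at r = 0.4 and 0.084 at r = 0.6, against about 0.01 with HbA1c added.

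**5. Validity of each model.** FBG-only: average bias at most 0.009 points, coverage 94.2–95.5%. With HbA1c added, base-case coverage is 93.7–96.1% (1,200 replicates per cell).

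**6. A side benefit.** Section 2.5.1 speaks of change in HbA1c, while 2.6.1 speaks of the difference in HbA1c at 3 months. Under the FBG-only model these give different estimates: with an assumed HbA1c SD of 1.6 they differ by a median of about 0.08 points, and by about 0.23 at the 95th percentile. With baseline HbA1c in the model the two estimates are algebraically identical.

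**The case against.** Several points can fairly be made for the plan as written.

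- **No error is shown.** The FBG-only estimate is about unbiased, its interval is valid and ±0.40 is correct. This stands, and it is why the point is minor.
- **The target is inferred.** The model sentence names no outcome, and 2.5.2.1 lists change in FPG as an endpoint, for which baseline FBG is the natural covariate. This also stands as a possible reading. On it, however, the primary endpoint has no specified model at all, and the same sentence repairs that.
- **HbA1c is already handled by matching.** Matching on HbA1c and adjusting for FBG, which is not in the propensity score, is a coherent division of work. It does limit average imbalance, but it leaves the residual imbalance shown above, and the plan has no response to a poor balance check. A wide within-pair gap is normal for propensity matching and is not in itself evidence of bias.
- **The gain is small and assumed.** It is nil at r = 0 and 0.4% at r = 0.2. Baseline laboratory values may be up to nine months old (2.2.5), which could weaken r. Measured against no covariate at all, the SD falls 1.6% (0.1920 to 0.1890) at r = 0.4 and 4.6% (0.1730 to 0.1650) at r = 0.6. Even in badly balanced replicates the mean error is 0.060/0.380 = 16% to 0.084/0.357 = 24% of the half-width. All of this stands.
- **Larger threats are untouched.** Unmeasured differences between prospective app users and retrospective specialty-clinic patients remain. True, but that is no reason to leave a measured one unadjusted.

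**Conclusion.** The point holds and is minor. The plan's only linear outcome model omits the baseline value of its primary outcome, and no other section supplies it. The omission invalidates neither the estimate, the interval nor the sample size. The loss is roughly 0–7% in the sampling SD, plus exposure to about 0.02–0.06 HbA1c points of error per 0.1 SD of leftover imbalance at correlations of 0.4–0.6. Those sizes rest on assumed correlations, control-pool size, pre-match shift and caliper; only 109 per arm and SD 1.5 come from the plan. The direction does not rest on them: at worst the added term costs one degree of freedom.

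**What to change.** In 2.6.2, before outcome data are analysed, replace the model sentence with one that names the outcome and both baselines, for example:

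*The 3-month change in HbA1c will be analysed by a linear mixed model with fixed effects for group, baseline HbA1c and baseline FBG, and a random intercept for matched pair.*

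State separately that the FPG-change endpoint uses baseline FBG as its main covariate.

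The cost is one model term and one degree of freedom, using a value already held for every eligible patient. Sample size, matching and data collection do not change.

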2.2.5 Study Calendar

Clinical Care/EMR Data Abstraction			
Demographics ⁵	Х		
Patient History ⁶	Х		
Vital signs ⁷	Х	Х	Х
Lab work ⁸	Х	Х	Х
Self-monitoring blood glucose (SMBG)		Х	Х
Provider visits (and Endocrinology escalation visits)		х	Х
Hypoglycemic events	Х	Х	Х
Hospital stays	Х	X	Х
Adverse events	Х	X	Х

1. Education on MDC-M app only for those participants who were able to reach target FBG/A1c transition to maintenance.

2. Diabetes Medication System Rating Questionnaire-Short Form (DMSRQ-SF), Diabetes Distress Scale (DDS17) at all time points; Usability and Satisfaction surveys as 3 and 6 months.

3. Health care provider perspectives and experiences on insulin dosing survey at baseline and usability and satisfaction survey at 3 months and completion of the study.

4. Participant name, age, gender, race, ethnicity, contact information, location, marital status, employment status, education level, health insurance information

5. Diabetes duration, diabetes-related medication, diabetes-related hospitalizations, hypoglycemic events within the past year, co-morbidities

6. Blood pressure, weight, BMI

7. Fasting blood glucose, HbA1c, cholesterol, lipids (if available in clinical records); baseline values may have been collected and recorded up to nine months prior to study start (e.g., lipid panels are usually conducted once a year).

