2.5.2 Secondary Endpoints

2.5.2.1 Phase 1 (Titration)

- Change in HbA1c from baseline to 3 months within and between groups
- Proportion of patients reaching HbA1c <7% at 3 months as compared to patients using SOC
- Change in FPG from baseline to 3 months within and between groups
- Patient-reported changes in behavioral and psychosocial outcomes from baseline to 3 months (survey)
- Patient-reported acceptability of and satisfaction with MDC-T (survey)
- Provider-reported acceptability of and satisfaction with MDC-T (survey)
- Rate of escalation to Endo (Endocrine visits) for patients using MDC-T
- Safety end points (including hypoglycemia, any untoward adverse events)
- Number and type of technical complaints

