3 HUMAN SUBJECTS

3.1 Subject Population

Intervention participants will be identified in a consecutive manner at participating UPMC community-based PC practices, outpatient clinics and inpatient units. Study participants will include adult male and female T2DM patients, 18 to 75 years old, with T2DM and suboptimal glycemic control (HbA1c > 7.5%) who are recommended to start titrating basal insulin and willing and able to use the MDC app.

The retrospective comparative group will be selected from eligible patients who previously were treated at the UPMC Diabetes Outpatient Clinics. This group will be chosen for two reasons. First, patients seen at the Diabetes Outpatient Clinic have the most robust data available regarding insulin titration, including HbA1c and FBG and, for many patients, BG meter readings. Secondly, this particular group establishes a standard of specialty care against which to compare MDC and will uniquely inform the benefit of MDC. Patients in the usual care group will be identified using EMR data accessed through the UPMC Clinical Data Warehouse.

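### The slope contrast planned for binary outcomes does not fit HbA1c <7% at 3 months: both groups start at 0% by design, so under a logit link the group-by-time term is not identified

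*Combined protocol and SAP*

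**What the plan says.** Section 2.6.2 gives one between-group method for binary outcomes. It is a GEE "for binary outcomes to compare the change in slopes of outcomes of interest between the two groups", with allowance for the matched pairs. The sentence states no link, time coding, working correlation or month-3 contrast.

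Section 2.5.2.1 lists the endpoint concerned: "Proportion of patients reaching HbA1c <7% at 3 months as compared to patients using SOC". It fixes one threshold, one time point and one comparator.

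Sections 3.2.1 and 3.2.2 both require HbA1c above 7.5% at entry, for the intervention and usual care groups respectively.

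The Phase 2 paragraph of section 2.6.2 is descriptive and limited to the intervention group. No later between-group data are planned that could supply a different slope.

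**The concern.** A slope to month 3 uses the baseline and month-3 values of the outcome. For HbA1c <7% the entry rule fixes the baseline value at zero in everyone, so baseline carries no information on how the groups differ. On the logit scale it also makes the slope in each group infinite. The contrast that the plan names is then the difference of two infinite quantities.

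What is at stake is a secondary endpoint, but one tied to the stated primary objective (section 1.1.1), which speaks of a greater chance of reaching glycemic control at 3 months than under usual care. An analyst would probably notice the failure. The plan names no other between-group binary model, however, so the contrast, link and effect measure would be settled after the data are seen, in an open-label comparison with retrospective controls. The point concerns HbA1c <7% only. Individualized targets are not forced to zero by the entry rule.

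**Working it through.** **Inputs from the plan.** Section 2.6.1: "With 109 patients in the interventional arm and 109 patients in the retrospective control arm", and "The expected standard deviation for the 3-months change from baseline in HbA1c is 1.5". Section 2.6.2: 1:1 matched pairs. Sections 3.2.1 and 3.2.2: entry HbA1c above 7.5%, hence 0/109 v 0/109 below 7% at baseline if the qualifying value is the baseline value.

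**Assumed.** The documents give no month-3 response rates. The main illustration is 44 v 27 of 109 (about 40% v 25%, intervention v usual care). Two other pairs of counts give the range.

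**1. The plan's own figure.** Half-width = 1.96 × 1.5 × √(2/109) = 0.398, which agrees with the stated ±0.40. It concerns continuous HbA1c and is not touched by this point. No precision is stated for the binary endpoint.

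**2. The slope contrast under a logit link.** The model has an intercept, group, time (baseline, month 3) and group × time:

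interaction = [logit p(int, month 3) − logit p(uc, month 3)] − [logit p(int, baseline) − logit p(uc, baseline)]

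The first bracket is ln(44/65) − ln(27/82) = −0.390 + 1.111 = 0.721. In the second bracket both logits go to minus infinity. Baseline logits that fit the zeros equally well (log-likelihood contribution within 0.0001 of 0) give quite different interactions:

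| Baseline logit, usual care | Baseline logit, intervention | Interaction |
|---|---|---|
| −15 | −15 | 0.72 |
| −15 | −20 | 0.72 + 5 = 5.72 |
| −20 | −15 | 0.72 − 5 = −4.28 |

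The information matrix has rank 2 for 4 parameters. The model-based SE of the interaction is √Σ 1/[109 p(1−p)] over the four cells. With 25% v 40% at month 3 and a common baseline probability of 10⁻³, 10⁻⁶ and 10⁻¹², it is 4.3, 135 and 135,457, so it has no finite limit.

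GEE fits show the same. Over 40 fits (four random pairings, two working correlations, five sets of starting values) the interaction ran from −2.08 to 7.90. All 40 were flagged as converged, and the SE was not computable in 18. Most of that spread reflects the chosen starting values. With software defaults, independence returned 0.72 but with a printed robust SE in the thousands, and exchangeable returned 0.68, 0.72, −1.79 and 0.80 in the four pairings.

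**3. The month-3 contrast from the same model.** Group + interaction was 0.7207 in all of a further 40 fits of the same layout. Under independence its robust SE was 0.275 to 0.319. Closed form: √(1/44 + 1/65 + 1/27 + 1/82) = √0.0873 = 0.296.

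**4. Identity link.** The baseline difference is 0 − 0, so the slope difference is the month-3 risk difference: 44/109 − 27/109 = 0.156.

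**5. A few patients below 7% at baseline.** With k v k of 109, treating the cells as independent, SE = √(2[1/k + 1/(109−k)] + 0.0873):

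| k in each group | SE of slope contrast |
|---|---|
| 1 | 1.45 |
| 2 | 1.05 |
| 3 | 0.88 |
| 5 | 0.71 |

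The month-3-only SE is 0.30. With 2 v 1 at baseline the baseline log odds ratio is ln(2/107) − ln(1/108) = 0.702, and the slope contrast falls from 0.72 to 0.02.

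**6. Month-3-only analysis** (closed-form intervals):

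| Assumed counts of 109 | Odds ratio (95% CI) | Risk difference (SE) |
|---|---|---|
| 44 v 27 | 2.06 (1.15 to 3.67) | 0.156 (0.063) |
| 33 v 22 | 1.72 (0.92 to 3.20) | 0.101 (0.058) |
| 55 v 38 | 1.90 (1.10 to 3.28) | 0.156 (0.066) |

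**The case against.** A reader might infer that the between-group effect on HbA1c <7% is unidentified, or that the planned GEE cannot estimate this endpoint at all. The documents do not support that. Section 2.5.2.1 defines the endpoint as a month-3 comparison, and step 3 shows that a logit model with a group-by-time term still delivers it as group + interaction. Only the interaction, which is the difference in slopes, is lost.

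Three further objections have some force. First, the plan states no link, and its sentence on GEE is garbled, so the four-parameter logit model is a reading of it. That stands as a condition on the point, but the slope wording fails under a logit link and is redundant under an identity link, so it needs changing in either case. Second, the widest spread of interaction estimates comes from starting values that an analyst would be unlikely to choose. That also stands. The case does not rest on the range, because the default fits give no usable interaction SE under independence and varying estimates under exchangeable. Third, once the slope wording is dropped, the endpoint definition and the matched-pair GEE largely dictate the replacement. That is true and makes the repair easy, but the link and the leading effect measure would still be open.

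The baseline may also not be exactly 0%. The study calendar (section 2.2.5) says "baseline values may have been collected and recorded up to nine months prior to study start", so the value used as baseline could differ from the qualifying one. Step 5 shows that this does not rescue the slope contrast.

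**Conclusion.** The point holds in a limited form. The contrast named in section 2.6.2 does not match the month-3 binary endpoint. With 0% v 0% at baseline it is not identified under a logit link. With a handful of baseline events it is finite but dominated by those cells, with an SE of 0.71 to 1.45 for 5 v 5 down to 1 v 1, against 0.30 for month 3 alone. The endpoint is analysable, but not by the contrast the plan names.

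This rests on a logit link, which the plan does not state, and on taking the qualifying HbA1c as baseline for the exact 0%. The numerical illustrations rest on assumed month-3 counts, but the non-identification does not depend on them. The text should be corrected before analysis. The point does not threaten the primary endpoint or its precision.

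**What to change.** For HbA1c <7%, replace the slope wording in section 2.6.2 with one specification:

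*GEE on the month-3 indicator, treatment group as the only term, matched pair as the cluster, logit link, robust SE; the odds ratio with 95% CI is the main measure, with the risk difference from the same model as a supporting measure.*

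Baseline HbA1c is already in the propensity score. If an adjusted model is wanted, label it a sensitivity analysis, so that the choice between adjusted and unadjusted results is not left open.

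The cost is wording only. The model uses the month-3 HbA1c already needed for the primary endpoint, keeps GEE and the matched pairs, and adds no patients, data or comparisons.

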1.1.3 Hypothesis

Patients using MDC-T will reach individualized fasting plasma glucose (FPG) and HbA1c targets and MDC-M will help patients to maintain glycemic targets at 6 months from baseline.

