2 RESEARCH DESIGN AND METHODS

2.1 Classification and Methodological Designs

This study is a 6-month open label non-randomized trial with a prospective intervention group and a retrospective usual care group that includes two phases: Phase 1 (titration) will be used to determine effectiveness of MDC-T during insulin titration after 3 months. This is followed by Phase 2 (maintenance), a 3-month observational period for patients from the intervention group who reach titration targets, to determine effectiveness of their use of the MDC-M in helping patients maintain their glycemic targets. An overview of the study design in shown in the following figure.

Figure 2.1. Study Design

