For those patients who do not reach target at 3 months, the DCES/HCP will partner with the patient (and physician provider, as needed) to assess the patient's ability and interest in continued use of the MDC-T app and determine the best course of action (either return to usual care or continued participation in the study). If deemed eligible, the patient will continue to have access to the MDC-T app with continued guidance from their respective HCP, in regards to insulin therapy recommendations. They will be asked to complete follow-up surveys at months 3 and 6, as well as permit access to pertinent medical record information (e.g., HbA1c values) for the duration of the study. Patients who stay in the study and continue to use the MDC-T app will receive another three-month supply of insulin pens (Lantus (U100) Solostar Pen or Toujeo (U300) Solostar Pen, as per treating Physician).

Phase 2 (Maintenance)

Patients who are successful in reaching their glycemic target and agree to continue participation, will be transitioned into Phase 2 of the study at their three-month clinic visit. At this time, the HCP (endocrinology provider and/or DCES) will introduce and train patients how to use the MDC-M app to support glycemic control. Patients will receive another three-month supply of insulin pens (Lantus (U100) Solostar Pen or Toujeo (U300) Solostar Pen (as per treating Physician) and asked to return for the final follow-up visit at six months (routine clinic visit). They also will be asked to complete follow-up surveys at months 3 and 6 to assess changes in behavioral and psychosocial factors that influence diabetes self-management as well as their acceptability and satisfaction with their experience using the MDC app. When possible, surveys will be completed at clinic visits. However, surveys may also be made available electronically or via mail should visits occur remotely (e.g., via telemedicine) or a patient cannot complete at a face-to-face visit (e.g., time constraints).

The DCES and endocrinology provider will be available throughout the course of the study to respond to any question or concerns that the patient may have regarding insulin titration, insulin dosing, and the MDC app specifically.

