Phase 2 (Maintenance): For the intervention group only, using a descriptive statistical approach, an assessment of maintenance outcomes will occur to compare the percentage of patients at goal between the study treatment group at 6 months. Clinician and patient experiences and perspectives on the usability of and satisfaction with MDC-M will be assessed through various means including study-specific efficiency and satisfaction surveys.

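### Phase 2 is said to determine the effectiveness of MDC-M, but it is analysed descriptively in intervention responders alone, so the retention percentage cannot be attributed to the app

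*Combined protocol and SAP*

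**What the plan says.** Three places give Phase 2 a causal aim. Section 1.1.3 hypothesises that "MDC-M will help patients to maintain glycemic targets at 6 months from baseline". Section 2.1 runs the phase "to determine effectiveness of their use of the MDC-M in helping patients maintain their glycemic targets". Section 2.4.1 states that "HbA1c will serve as the primary outcome to determine the longer term impact of MDC-M app on maintenance of glycemic control".

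The population is one selected arm: Section 2.1 defines Phase 2 as "a 3-month observational period for patients from the intervention group who reach titration targets". The analysis in 2.6.2 matches that population: "For the intervention group only, using a descriptive statistical approach, an assessment of maintenance outcomes will occur". The same sentence then sets out to "compare the percentage of patients at goal between the study treatment group at 6 months". The two proportion endpoints in 2.5.2.2 set month 6 against month 3. Section 2.5.2.1 names between-group contrasts for the Phase 1 change in HbA1c and FPG; 2.5.2.2 names none for Phase 2.

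On 6-month data outside this group, 2.4.1 plans to select controls with HbA1c at baseline and at "follow-up time points/time frames that correspond with those described in the study calendar", and the calendar in 2.2.5 ends at 6 months. Section 3.2.2, however, admits a control with a baseline value and one later value. Under 2.2.3, intervention patients who miss target but stay in the study are asked to "permit access to pertinent medical record information (e.g., HbA1c values) for the duration of the study"; others may return to usual care. Section 10 says nothing more is collected after withdrawal.

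**The concern.** Effectiveness means a difference from what would have happened without the app. The planned result is a single percentage: of those at goal at month 3, how many are at goal at month 6. Nothing in the plan says what that percentage would be under usual care. No comparator or benchmark is given, and nothing allows for patients having been selected on the month-3 value.

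That selection matters because some patients are below target at month 3 partly by chance, and their next value tends to be higher. Some loss of goal is therefore expected even if the app does nothing and true control is stable. A reader who takes 2.1 at its word could treat 85% retention as evidence for MDC-M, or 80% as evidence against it. Both readings would be unfounded.

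The 2.6.2 sentence adds a practical problem. It restricts the analysis to one group and then asks for a comparison between groups, so two analysts could implement it differently.

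**Working it through.** **The plan's own figures (2.6.1).** SD of the 3-month HbA1c change is 1.5, with 109 per arm.
- Half-width = 1.96 × 1.5 × √(2/109) = 0.398, which agrees with the stated ±0.40.
- Phase 2 entry = 0.70 × 109 = 76.3, which agrees with n=76.

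Both figures reproduce. The sample size is justified by the 3-month difference and not by any Phase 2 contrast.

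**Loss of goal with no app effect.** The documents give no correlation between month-3 and month-6 HbA1c, so it is assumed. The model is bivariate normal with the same distribution at both times, a proportion p at goal at month 3, and correlation r. With c the standard normal quantile of p:
- retention = P(Z₆ < c and Z₃ < c) / p
- mean rise among responders, in SD units = (1 − r) × φ(c) / p

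For p = 0.70, c = 0.524 and φ(c)/p = 0.497.

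| Assumed r | Still at goal at month 6 | Lost goal | Mean rise (SD) |
|---|---|---|---|
| 0.7 | 84.4% | 15.6% | 0.15 |
| 0.8 | 87.3% | 12.7% | 0.10 |
| 0.9 | 91.1% | 8.9% | 0.05 |

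Among 76 patients this is 76 × 0.089 = 6.8 to 76 × 0.156 = 11.9, or about 7 to 12 losing goal by regression alone. A weaker correlation of 0.5 gives a 20% loss.

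**What the planned estimate would show.** Wilson 95% intervals with n=76:
- 61/76 (80%): 70% to 88%
- 68/76 (89%): 81% to 95%

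Both intervals overlap the no-effect range of 84% to 91%.

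**Responders against responders.** Assume 80% retention in each group, 76 intervention responders, and 33 to 76 control responders (about 30% to 70% of 109).
- 33 controls: 1.96 × √[0.16 × (1/76 + 1/33)] = 0.163
- 76 controls: 1.96 × √[0.16 × (1/76 + 1/76)] = 0.127

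The half-width is therefore about 13 to 16 percentage points.

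**All matched pairs at 6 months.** If the SD of the 6-month change is also 1.5 (an assumption) and all values are present, the half-width is again 0.398. With an assumed 10% to 20% missing in each group, replacing 109 by 98.1 to 87.2 gives 0.42 to 0.45.

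**The case against.** The strongest reply is that Phase 2 was meant to be descriptive. Section 2.1 calls it observational. The primary objective (1.1.1) and Aim 2 (1.2.2) ask only whether patients can maintain control, and the proportion endpoints in 2.5.2.2 are within-group. On that reading the group wording in 2.6.2 is a drafting slip. This largely stands: the plan can answer the descriptive question. It does not rescue the effectiveness wording in 1.1.3, 2.1 and 2.4.1, which then needs to come into line.

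A reader might also infer four stronger points that the documents do not support.
- *That 6-month control data are already secured, so a controlled comparison needs nothing new.* Section 2.4.1 points that way, but 3.2.2 requires only one value after baseline. Month-6 values are also not assured for intervention patients who return to usual care or withdraw.
- *That adding controls would isolate MDC-M.* Phase 2 patients have also used MDC-T and receive supplied insulin (2.2.3, 11.1). The contrast would test the whole strategy.
- *That selecting responders flatters the app.* Selection on a low month-3 value raises the expected month-6 value, so retention looks worse.
- *That regression alone could cost up to about 37% of responders.* That figure needs a month-3 mean as high as 7.5%. The assumptions behind a 14% to 37% range (mean 7.0% to 7.5%, SD 0.9 to 1.1) put only 29% to 50% of patients below 7%, which does not fit the plan's 70%.

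**Conclusion.** The point holds as a mismatch between aim and analysis. Carried out exactly as written, Phase 2 yields a retention percentage in selected patients with no reference value, and that cannot establish an effect of MDC-M. At the plan's 70% and an assumed correlation of 0.7 to 0.9, about 9% to 16% would lose goal by regression to the mean alone, with bias against the app. These figures rest on a bivariate-normal model with a stable distribution. They treat the 70% entering Phase 2 as the share at goal, and they apply one threshold where entry is by individualized target.

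The 3-month primary endpoint and its sample size are unaffected. The change should be made because maintenance is part of the stated primary objective and the correction is cheap.

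**What to change.** 1. In 2.6.2, rewrite the Phase 2 sentence so that it names one group and one contrast: the proportion of patients at goal at month 3 who remain at goal at month 6, with a 95% CI. Reword 1.1.3, 2.1 and 2.4.1 so that Phase 2 describes this proportion and makes no effectiveness or impact claim for MDC-M.

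2. Reconcile 2.4.1 with 3.2.2 by stating whether a control must have a 6-month HbA1c. Requiring one may shrink the control pool and select controls by continued follow-up.

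3. Where 6-month values exist, add to 2.6.2 a between-group comparison of the 6-month HbA1c change over the matched pairs, using the two-group mixed model already specified there. Report missing month-6 values in both groups and state how they are handled. Label the result as the whole MDC-T/MDC-M strategy against usual care.

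4. Retention below 7% among month-3 responders in each group may be shown as supportive only. It conditions on a post-treatment response, breaks the matching, and is imprecise (about ±13 to ±16 points).

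The cost is wording changes in four sections, a reconciled control-data rule and one extra analysis. The 6-month control data may prove incomplete, and the stated aim of Phase 2 becomes more modest.
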